2.5.4 Safety Analysis

Section 6.4.5 outlines all potential SAE's and defines a SUAE as any SAE that occurs in the setting of $\text{MetHb} > 10\%$ which may thus be attributed to the study drug. All listed safety outcomes will be tabulated and summarized using basic descriptive statistics and tested using small sample exact methods.

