6.4.5 Reportable Adverse Events

This is a high risk population in which numerous serious adverse events are expected. Indeed, all subjects will require mechanical ventilation, with >50% of subjects expected to require >50% FiO₂ and/or vasopressors during the first 24 h based on our prior data^{33,34} and expected mortality is 70-80%³⁵ as we are excluding non-comatose subjects. Thus numerous serious adverse events (SAE) are anticipated during the conduct of this study with a complete list provided below. In this context we define a SUAE as any SAE that occurs in the setting of MetHb > 10% which may thus be attributed to the study drug.

Expected SAE (with severity grade indicated)

- Non-central nervous system thrombosis, particularly in vessels accessed for endovascular devices, assessed as symptomatic venous or arterial thrombus documented radiographically or ultrasonographically. (Grade 3)
- Sepsis assessed as the presence of microbiologically proven, clinically proven, or suspected infection; presence of Systemic Inflammatory Response Syndrome (SIRS); and development of at least one organ dysfunction within the preceding 24 hours. Diagnosis of SIRS will require the fulfillment of at least two of the following criteria (Grade 4):
 - Hyperthermia ($\geq 38^{\circ}\text{C}$) (which will only be evident after active temperature control);
 - Tachycardia ($\geq 90 \text{ bpm}$);
 - Tachypnea ($\geq 20 \text{ breaths/min}$) or an arterial pCO₂ $\leq 4.3 \text{ kPa}$ (32 mmHg) or mechanical ventilation;
 - White blood cell count $\geq 12,000/\mu\text{L}$ or $\leq 4,000/\mu\text{L}$ or left shift in differential white blood cell count $\geq 10\%$.
- Expected organ dysfunctions after OHCA (which may accompany SIRS in sepsis as defined above or separately) will be defined as:
 - Acute encephalopathy not explained by psychotropic medication (or attributable to the cardiac arrest) [Grade 3];
 - Thrombocytopenia $\leq 100,000/\mu\text{L}$ or drop in platelet count $> 30\%$ within 24 hours not explained by hemorrhage (Grade 3);
 - Arterial hypoxemia with an arterial pO₂ $< 8 \text{ kPa}$ (60 mmHg) when breathing room air or an oxygenation index (paO₂/FiO₂ $\leq 200 \text{ mmHg}$) not explained by presence of a pulmonary or cardiac disease (Grade 4);

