 - Arterial hypotension with a systolic blood pressure $\leq 90 \text{ mmHg}$ or mean arterial blood pressure $\leq 65 \text{ mmHg}$ for at least one hour despite adequate fluid loading not explained by other causes of shock (Grade 4);

- Renal dysfunction with urine output ≤ 0.5 mL/kg/h for at least one hour despite adequate fluid loading or serum creatinine above 200 $\mu\text{mol/L}$ (2.3 mg/dL) [Grade 3];
 - Metabolic acidosis with base deficit ≥ 5.0 mmol/L or serum lactate ≥ 1.5 fold above local reference range (2.4 mmol/L at UPMC) [Grade 3].
- Pneumonitis assessed as the presence of air bronchograms on any chest x-ray within one week of the index cardiac arrest. (Grade 3)
- Since many of these comatose OHCA subjects will receive therapeutic hypothermia, anticipated SAE include:
 - Electrolyte abnormalities: defined as the presence of any of the following from induction of hypothermia until 72 hours (all Grade 3):
 - Hypokalemia assessed as serum potassium concentration < 3.5 mmol/L.
 - Hyperglycemia assessed as serum glucose > 240 mg/dL.
 - Hypophosphatemia assessed as serum phosphate concentration < 0.8 mmol/L.
 - Hypocalcemia assessed as serum ionized calcium < 2.2 mmol/L.
 - Bleeding (overt bleeding with Hb drop > 3 g/dL or transfusion; cardiac tamponade; bleeding requiring surgical intervention for control or intravenous vasoactive agents; intracranial hemorrhage; intraocular bleed compromising vision; operation for vascular closure for the purpose of controlling bleeding; fatal bleeding) [Grade 3]
 - Thrombosis (Grade 3)
 - Infection (Grade 3)
 - Fluid shifts defined as net fluid intake/output exceeding 3 L positive or negative in a 24h period (Grade 3)
- Pulmonary Edema: We shall monitor the incidence of pulmonary edema in each treatment duration group and assess whether there is a significant difference between groups. It will be defined as the presence of congestive heart failure on a hospital-based chest x-ray (first emergency department or ICU chest x-ray). OHCA is more common in patients with cardiomegaly, and this radiographic sign alone will not be a criterion for diagnosis of acute heart failure. (Grade 3)

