- Other common post-OHCA SAE (Grade 3 unless specified) include pneumonia, cerebral bleeding, stroke, seizures, bleeding requiring transfusion or surgical intervention, rearrest (Grade 5), rib fractures, sternal fractures, internal thoracic or abdominal injuries as well as any other major medical or surgical outcomes will be recorded as noted in the hospital discharge summary.

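### The SAE comparison has no common observation window, so a survival difference between arms can distort the counts for SAEs with no fixed end.

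*Combined protocol and SAP*

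**What the plan says.** Section 2.5.4 identifies the outcomes ("Section 6.4.5 outlines all potential SAE's") and then gives the whole method: "All listed safety outcomes will be tabulated and summarized using basic descriptive statistics and tested using small sample exact methods". It names no unit of analysis, follow-up window, person-time denominator or treatment of death as a competing event. Section 2.5.2 names Kaplan-Meier and log-rank methods for time-to-event endpoints but assigns them to no safety outcome.

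The observation periods in section 6.4.5 differ by outcome:

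- **No stated end:** sepsis, non-CNS thrombosis, bleeding, organ dysfunction. The sepsis definition asks for "development of at least one organ dysfunction within the preceding 24 hours", which concerns onset and does not close the window.
- **From the discharge summary:** the group with pneumonia, stroke and seizures, where "any other major medical or surgical outcomes will be recorded as noted in the hospital discharge summary".
- **Fixed and early:** pneumonitis (one week), pulmonary edema (first ED or ICU film) and electrolytes, "defined as the presence of any of the following from induction of hypothermia until 72 hours". The last has no starting point for a subject who is not cooled.

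On pulmonary edema, the section plans to monitor incidence "in each treatment duration group and assess whether there is a significant difference between groups". Section 2.1 randomises 1:1 to iNO or placebo, and section 2.3.2 gives every patient the same administration pattern, so the trial has no duration groups.

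The same section says "and expected mortality is 70-80" (per cent). Section 1.2 states the hypothesis that iNO reduces death.

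**The concern.** An SAE with no closing day can be counted only while the patient is alive and in hospital. If most patients die, and one arm dies less, that arm contributes more days in which an event can occur. At the same daily risk, more of its subjects will have an event. A beneficial drug then looks more toxic in the SAE table. In the other direction, a drug that raises both SAE risk and mortality can show nearly equal proportions. The DSMB is charged in section 6.4.2 with weighing risk against benefit, so the SAE table should not itself be driven by survival.

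**Working it through.** **The plan's own figure.** There is none for safety. The only planned effect size is in section 2.5.1: about 23 points on the composite, 60 per arm, power above 80%. Reading the 5% there as two-sided alpha,

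power = Φ{[Δ√n − 1.96√(2p̄q̄)] / √(p₁q₁ + p₂q₂)}.

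For 80% against 57%, n = 60: (1.782 − 1.288)/0.636 = 0.776, so power is 0.781. It is 0.801 from 82.5% and 0.823 from 85%, so the figure reproduces to within 2 points. It concerns the composite, not mortality.

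**Inputs for the check.** From the documents: mortality 70-80% (midpoint 75%) and 65 per arm. Assumed: time observed for those who die (Td) and survive (Ts), and a daily SAE hazard h that is equal in both arms. With m the arm's mortality,

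share with an SAE = m(1 − e^(−h·Td)) + (1 − m)(1 − e^(−h·Ts)).

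**Example, Td = 4, Ts = 14, h = 0.05/day.**

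- Placebo, m = 0.75: 0.75 × 0.181 + 0.25 × 0.503 = 26.2%.
- iNO, m = 0.52: 0.52 × 0.181 + 0.48 × 0.503 = 33.6%.
- False excess: 7.4 points. Mean observed days: (0.75 × 4 + 0.25 × 14) = 6.5 against (0.52 × 4 + 0.48 × 14) = 8.8, a ratio of 1.35.

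**Range.** Over (Td, Ts) = (3,10), (4,14), (5,12), (7,14) and h = 0.02, 0.05, 0.10:

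| iNO mortality | False excess | Observed-time ratio |
|---|---|---|
| 52% | 2.6 to 9.7 points | 1.18 to 1.35 |
| 60% | 1.7 to 6.4 points | 1.12 to 1.23 |

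**A second model.** Constant death hazard μ = −ln(1 − m)/21 over an assumed 21-day stay, SAE hazard 0.05/day, and cumulative incidence to day T = h/(h + μ) × (1 − e^(−(h+μ)T)):

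| Window | Placebo (75% die) | iNO (52% die) | False excess |
|---|---|---|---|
| 3 days | 12.7% | 13.2% | 0.6 |
| 7 days | 24.0% | 26.4% | 2.4 |
| 21 days | 39.3% | 49.0% | 9.6 |

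(Differences are taken before rounding.) Masking: if iNO raises the SAE hazard by 30% (to 0.065/day) and mortality is 85%, the 21-day shares are 39.3% and 40.2%. With mortality equal at 75%, iNO would show 46.4%.

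**SAE risk concentrated early.** Same (4,14) days, hazard 0.10/day to day 3 and 0.02/day after, in both arms. Cumulative hazard is 0.3 + 0.02 = 0.32 by day 4 and 0.3 + 0.22 = 0.52 by day 14.

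- Shares at 75% and 52% mortality: 30.7% and 33.7%, a 3.0-point excess. With 0.20/day early: 48.6% and 50.9%, 2.2 points. At 60% mortality the excess is 1.5 to 2.0 points.
- Events per patient-day, 0.10/day early: placebo (0.75 × 0.32 + 0.25 × 0.52)/6.5 = 0.0569; iNO (0.52 × 0.32 + 0.48 × 0.52)/8.8 = 0.0473; ratio 0.83 with no true difference. Over these scenarios the ratio is 0.79 to 0.88.

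**Chance of a significant result.** With Fisher's test at 65 per arm, the 26.2% against 33.6% example declares iNO worse in about 11% of trials, and in about 6% if iNO mortality is 60%. The rate is 1.6% when mortality is equal. In the 21-day model it is 14.8%, against 1.7%.

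**The case against.** Much of the opposing case stands.

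- **The unit and the windows are partly inferred.** Section 2.5.4 does not say that subjects are counted, and exact methods exist for rates too. A reader might infer that most SAEs are counted to death or discharge. The documents support that only for the group tied to the discharge summary; for sepsis, thrombosis, bleeding and organ dysfunction they are silent. Many of the defining data (new infection, creatinine, platelets, SOFA) are on the Day 1-3 list in section 2.2.
- **The trial is not sized on mortality.** A reader might take the 23-point effect as a planned fall in deaths. Section 2.5.1 applies it to the composite, so 75% to 52% is an upper case.
- **Equal risk per day is an assumption.** Rib and sternal fractures come from resuscitation. Rearrest, hypotension and acidosis can precede death, so for these the direction may weaken or reverse. Early concentration of risk cuts the artefact to about 2-3 points.
- **A patient-day rate ratio is not a clean cure.** As shown above, it can falsely favor iNO because its extra days are late and low-risk.
- **Hastened death would not go unseen.** A reader might conclude that a harmful drug would pass as safe. Death is in the primary composite, survival is a secondary endpoint at discharge, 30 and 90 days, and the safety monitor and DSMB review outcomes and may unblind.

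None of this supplies a common window for the open-ended SAEs.

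**Conclusion.** The gap is real and moderate. For SAEs with no stated end or taken from the discharge summary, the planned comparison can mix toxicity with survival. The size is about 3-10 points at 52% iNO mortality, 2-6 points at 60%, and 2-3 points with early-concentrated risk. These figures rest on assumed stays and hazards and on counting subjects with an event. Pneumonitis, first-film pulmonary edema and electrolytes to 72 h are little affected. The masking concern applies to the SAE table, not to the trial's ability to detect excess death.

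The reference to duration groups needs correcting in any case. It might be read as grouping patients by whether the gas was stopped early, but nothing in the documents says so; it is best taken as a wording error. The missing electrolyte window for uncooled subjects is a separate definitional gap, unrelated to survival.

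**What to change.** - **Section 2.5.4:** make the lead harm comparison one common window for every subject, from study drug start to 72 h post-ROSC, by randomised arm. The Day 1-3 data in section 2.2 already cover 0-72 h post-ROSC. Show deaths in the window beside each SAE, or report death-or-SAE. State that the unit is subjects with at least one event.
- **Later events:** tabulate those up to discharge separately and descriptively, with days alive in hospital by arm. Do not make the events-per-patient-day rate ratio the lead test.
- **Section 6.4.5:** compare pulmonary edema by randomised arm, and apply the electrolyte window to every subject whether or not cooled.

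The cost is SAP wording and one additional table, with no extra subjects or visits. There are two downsides. Late events leave the lead comparison. SAE onset must also be dated well enough to place it inside or outside the window; section 2.2 lists date and time of death but no SAE onset date, so a field may be needed.

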2.5.5 Handling Missing Data

Since our primary endpoint is ascertained at hospital discharge we expect no missing data though all analyses will be performed assuming a missing at random mechanism. No data imputation will be performed though standard sensitivity analyses, using standard missing data techniques may be used.

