The following data elements will be collected during the course of the study at the times indicated. Data elements marked with an asterisk indicate variables or outcomes essential for conduct of the study and analysis of efficacy and/or safety. These data elements should be obtained in all subjects with no missing data expected. In addition to these data elements, we are collecting a large amount of secondary data intended for use in mechanistic studies and hypothesis generation. In many cases, these data elements WILL NOT be able to be collected in all subjects. Such missing data will be handled as designated within an a priori statistical analysis plan but the presence of missing data will in no way impede our ability to meet the objectives of this phase 2 RCT.

BASELINE DATA

- *Date of OHCA
- *Time of OHCA (If not available we will use Time of ROSC after subtracting estimated no flow and CPR time based on transfer records/physician report)
- Witnessed
- Bystander CPR
- EMS Call Date
- EMS Call Time
- EMS Arrival Date
- EMS Arrival Time
- No flow time
- CPR (low flow) time
- Presenting rhythm
- *Date and Time of ROSC (If not available we will use ED admission date/time from referring hospital record. If unavailable, stat medevac call date/time minus 30 mins. If unavailable, time of arrival minus 15 min)
- PCAS ID
- *Last name
- *First name
- *Date of Birth
- *Medical record number
- Marital status
- Race/Ethnicity
- *Male Sex
- *Height
- *Weight
- Post-resuscitation chest pain

- Charlson Comorbidity
- Age Adjusted for Charlson Comorbidity Index (CCI)
- *New York Heart Association (NYHA) class pre-OHCA (if no surrogate is present and no medical records are found on the subject this will be assumed to be NYHA class I)
- Barthel ADL pre-OHCA
- Education level
- Private insurance
- Medicare
- Medicaid
- Employed
- Active smoker
- Smoker >20 pack-years
- Prior stroke
- Prior Coronary artery bypass grafting (CABG)
- Noninsulin-dependent diabetes mellitus (NIDDM2) type 2
- Insulin-dependent diabetes mellitus (IDDM2) type 2
- Diabetes mellitus (DM1) type 1
- Prior myocardial infarction (MI)
- Congestive Heart Failure (CHF)
- Chronic Obstructive Pulmonary Disease (COPD)
- Prior cardiac arrest
- Dementia
- Hyperlipidemia
- Hypertension
- Prior coronary stent
- Obstructive sleep apnea
- Pulmonary hypertension
- *Location pre-OHCA

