2.5.2 Study Conduct Analysis

Continuous data will be summarized and compared using t-tests or a non-parametric equivalent should the normality assumption appear tenuous. Generalized linear mixed models, which account for non-independence of repeated assessments and endpoint structure, will be used to compare between iNO and placebo groups at multiple times. Analysis of the composite endpoint will be ascertained using an unadjusted two sample test of proportions with a type II error rate of 5%. In the event of imbalance of potential confounders after randomization an adjusted analysis will be performed using logistic regression with those unbalanced variables and treatment as the main effect of interest. Other secondary dichotomous outcomes will be summarized and compared by chi squared tests and appropriate exact methods should sample sizes be small. Time to event endpoints will be summarized by Kaplan Meir curves and compared using log rank tests. All tests will be two tailed with unadjusted $p < 0.05$ considered significant and performed using SAS 9.4.

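### If imbalance triggers the adjusted analysis of the composite, the ban on imputation drops subjects with a known outcome whenever an unbalanced arrest covariate is missing

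*Combined protocol and SAP*

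**What the plan says.** Three parts of the combined protocol and SAP bear on this.

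- **Section 2.5.2 (Study Conduct Analysis).** The primary analysis uses no covariates: "Analysis of the composite endpoint will be ascertained using an unadjusted two sample test of proportions". A second analysis is conditional: "In the event of imbalance of potential confounders after randomization an adjusted analysis will be performed using logistic regression with those unbalanced variables". No covariate is named in advance.
- **Section 2.5.5 (Handling Missing Data).** The outcome is expected to be complete, with an ignorable mechanism assumed throughout: "Since our primary endpoint is ascertained at hospital discharge we expect no missing data though all analyses will be performed assuming a missing at random". The rule that follows is "No data imputation will be performed though standard sensitivity analyses, using standard missing data techniques may be used". It makes no distinction between outcomes and baseline covariates, and the sensitivity analyses are optional and unspecified.
- **Section 2.2 (Detailed Description of Study Design).** Elements marked with an asterisk are the essential ones: "These data elements should be obtained in all subjects with no missing data expected". Of the remaining data it says: "In many cases, these data elements WILL NOT be able to be collected in all subjects". It adds: "Such missing data will be handled as designated within an a priori statistical analysis plan". The only text supplied on that handling is section 2.5.5.

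In the baseline list, witnessed status, bystander CPR, no-flow time, CPR time, presenting rhythm and Charlson index have no asterisk. Date of birth, sex, and pre-arrest NYHA class, CPC, mRS and location do.

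**The concern.** A logistic regression fitted without imputation uses only subjects who have a value for every covariate in the model. If an unbalanced variable is one of the unstarred arrest covariates and has gaps, following section 2.5.5 as written deletes randomised subjects whose composite outcome is known.

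Two things are at stake. The adjusted estimate loses precision in a trial with little power to spare. It also rests on a different set of subjects from the unadjusted result, so a difference between the two could reflect the adjustment or the change of subjects. This matters because the adjusted model is the plan's only stated response to imbalance in the endpoint that section 2.5.3 relies on to show efficacy.

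Some missing arrest history is plausible from the protocol itself. Section 2.3.3 says that most patients at the larger centre arrive by transfer 1 to 3 hours after ROSC, and that many come without family. Section 2.2 needs fallback rules even for the starred times of arrest and of ROSC.

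**Working it through.** **1. The plan's own figure.** Inputs from section 2.5.1: control event rate 80–85%, reduction of about 23 (read as percentage points), 60 evaluable per arm, 65 per arm after 5% dropout. The 5% error rate is read as a two-sided significance level, in line with the two-tailed 0.05 rule in section 2.5.2.

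Power = Φ{[d√n − 1.96√(2p̄(1−p̄))] / √(p₁(1−p₁) + p₂(1−p₂))}, with n per arm, d = p₁ − p₂ and p̄ the mean of p₁ and p₂.

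- p₁ = 0.80, p₂ = 0.57, n = 60: (1.782 − 1.288)/0.636 = 0.776, so power is 78.1%.
- p₁ = 0.85, p₂ = 0.62, n = 60: (1.782 − 1.223)/0.603 = 0.927, so power is 82.3%.
- At a control rate of 82.5%, power is 80.1%.

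The stated 80% is reproduced at mid-range. With 65 per arm, power is 81.3% to 85.2%. Dropout: 60/0.95 = 63.2, rounded up to 64, against 65 stated.

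**2. Subjects left in the adjusted model.** The number of incomplete covariates (four) and the missing rate m for each are assumptions. If values go missing independently, N = 130 × (1 − m)⁴. If the same subjects lack all four, N = 130 × (1 − m).

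- m = 5%: 130 × 0.8145 = 105.9 (independent); 130 × 0.95 = 123.5 (full overlap).
- m = 10%: 130 × 0.6561 = 85.3 (independent); 130 × 0.90 = 117 (full overlap).

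A common cause, such as having no informant, would push the result towards the overlap end. A single incomplete covariate gives the same counts as full overlap.

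**3. What that costs in power.** The formula in step 1 with n = N/2 serves as an approximation to the adjusted model, for a 23-point difference.

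| Subjects analysed | Control 80% | Control 85% |
|---|---|---|
| 130 | 81% | 85% |
| 123.5 | 79% | 83% |
| 117 | 77% | 81% |
| 105.9 | 73% | 77% |
| 85.3 | 63% | 68% |

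**4. Bias.** A logistic model was simulated with 400,000 subjects, one prognostic covariate, a true treatment log odds ratio of −1.2, and event rates of 83% and 64%. The adjusted log odds ratio was −1.197 with complete data. The complete-case value was −1.192 when the covariate was missing at random in 20%, −1.194 when missingness depended on the covariate, and −1.199 when it depended on the outcome alone. It moved to −1.374 only when missingness depended on outcome and arm together.

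**5. Consistency within the plan.** Section 2.2 sets unknown pre-arrest status to NYHA class I, CPC 1 and mRS 0. That is single-value imputation, which section 2.5.5 rules out. The NYHA default also feeds the primary endpoint, because section 2.4 requires a worsening of at least one class where heart failure already existed.

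**The case against.** The strongest case against is that the problem may never arise. The primary test needs no covariates. The adjusted model runs only after imbalance, and only with the unbalanced variables; if those are starred items such as age or sex, nobody is expected to be lost. All of this stands.

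A reader might infer that the protocol says arrest covariates will often be missing. It does not. The statement in section 2.2 covers the unstarred data as a whole and gives no rate. The only items described as frequently unavailable are pulmonary artery pressures, central venous pressure and SvO2. Section 2.2 also says that most baseline items can be collected retrospectively, and its fallback for the time of arrest presumes estimates of no-flow and CPR time. Section 5.1 has physicians review the arrest before enrolment. CPR duration should be roughly known for everyone, because section 3.2 limits entry to ROSC within 40 minutes of starting CPR.

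A reader might also infer that the complete-case estimate is biased. The documents do not support that. An unwitnessed arrest or an absent family precedes randomisation, so the resulting gaps should not differ by arm, and step 4 shows almost no movement in that situation.

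Finally, sections 2.2 and 2.5.5 do promise advance handling and permit sensitivity analyses. But nothing there is mandatory or specific, so the deletion of subjects stands as the written rule. An adjusted odds ratio also differs from an unadjusted one with complete data, because the odds ratio is non-collapsible. Keeping all subjects removes one source of difference, not both.

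**Conclusion.** The point holds as a conditional weakness of the adjusted analysis. It is not a fault in the primary analysis. It applies if imbalance triggers the logistic regression and at least one unbalanced variable is an unstarred covariate with missing values.

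The size cannot be fixed from the documents. Under the assumed four covariates, the loss runs from about 6 of 130 subjects (5% each, full overlap) to about 45 (10% each, independent). Approximate power falls from 81–85% to 79–83% in the first case and to 63–68% in the second. One covariate missing at 5% costs about 2 points of power.

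The harm is lost precision and a changed set of subjects. Bias would need missingness that depends on arm and outcome together, and nothing in the documents suggests that. This is a cheap improvement worth making, and it leaves the primary result untouched.

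**What to change.** Amend section 2.5.5 to say:

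- Outcomes are not imputed.
- Missing baseline covariates in the adjusted model are filled by a rule fixed in advance and applied blind to arm and outcome: the overall mean, or a separate missing category for categorical items where numbers allow.
- Every randomised subject with an outcome enters the adjusted model. The complete-case result is reported as a sensitivity analysis.
- The defaults in section 2.2 for unknown pre-arrest NYHA class, CPC and mRS are stated as exceptions or otherwise reconciled with this rule.

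The cost is a few sentences and no new data. In a simulation of 130 subjects, mean imputation raised the adjusted model's power from about 83–84% to 85% with one covariate missing at 5%. With three covariates at 10% each it rose from 70% to 83% (independent) or from 79% to 82% (overlapping). These gains depend on the simulated covariate effects.

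There are two drawbacks. Filling covariates in a logistic model moves the conditional odds ratio slightly towards the null: at 5–10% missing, the log odds ratio shrank by about 0.5–4% in simulation. Each missing category also adds a parameter. At the planned rates only about 34 to 41 subjects would be event-free (65 × 0.15 + 65 × 0.38 = 34; 65 × 0.20 + 65 × 0.43 = 41), so such categories should be used sparingly.
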